2.3.2 Demographics and other baseline characteristics

The FAS will be used for all baseline disease characteristics and demographic summaries and data listings.

2.3.2.1 Demographics

Demographic data will be listed in detail. Quantitative data (e.g., age) will be summarized by appropriate descriptive statistics (n, mean, standard deviation, median, minimum, and maximum).

2.3.2.2 ECOG status

ECOG performance status will be summarized (n and %, missing if any).

2.3.2.3 Diagnosis and extent of cancer

Diagnosis and extent of cancer for each patient will be listed. This listing will include the following: primary site of cancer, histological grade, stage at initial diagnosis, time since initial diagnosis, time from initial diagnosis to first recurrence/progression, stage at time of study entry, presence/absence of target and non-target lesions, number and type of metastatic sites involved, HER-2 / estrogen / progesterone receptor status, number of de novo patients, disease free interval (DFI) for non-de novo patients and prior endocrine therapy status (ET).

Estrogen and progesterone receptor status summary will be combined into 3 categories (ER+, PR+, ER+ PR-, ER- PR+).

2.3.2.4 Medical History

Medical history and ongoing conditions, including cancer-related conditions, will be listed. Medical history/current medical conditions are coded using the latest version of Medical Dictionary for Regulatory Activities (MedDRA) terminology available at the time of the analyses. The MedDRA version used for reporting will be specified in the CSR and as a footnote in the applicable listings.

2.3.2.5 Study treatment

Duration of study treatment exposure, cumulative dose, dose intensity (DI) and relative dose intensity (RDI) will be summarized. The number of patients with dose reductions/interruptions, and the reasons, will be summarized and listed. Details of the derivations and summaries are provided in the following sections.

The safety set will be used for all summaries and listings of study treatment.

Duration of study treatment exposure

The duration of exposure to study treatment will be calculated as Duration of exposure to study treatment (days) = (last date of exposure to any study treatment component) – (date of first administration of study treatment) + 1.

Duration of exposure to alpelisib (days) = (last date of exposure to alpelisib) – (date of first administration to alpelisib) + 1.

Duration of exposure to fulvestrant (days) = (last date of exposure to fulvestrant) – (date of first administration to fulvestrant) + 1.

The last date of exposure is defined as follows for the study treatment components:

For alpelisib: the last date of exposure is defined as the date of last administration of the corresponding medication;

For fulvestrant, the last date of exposure is defined as following:

If patient discontinues fulvestrant before C2D1 dose, then:

- Last date of exposure = last date of administration + 13 days.

If patient died or lost to follow-up within last date of administration + 13 days,

- then last date of exposure is date of death or last contact date, respectively.

If patient discontinues fulvestrant after C2D1 dose, then:

- Last date of exposure = last date of administration + 27 days.

If patient died or lost to follow-up within last date of administration + 27 days,

- then last date of exposure is date of death or last contact date, respectively.

The duration of exposure includes the periods of temporary interruption (of any component of the study treatment for any reason). The duration of study treatment exposure will be summarized. In addition, the duration of exposure to study treatment will be

categorized into time intervals (. < 1 month, 1- 2 months, 2 to 3 months, 3 to 4 months, 4 to 6 months, 6 to 8 months, 8 to 10 months and \geq 10 months); frequency counts and percentages will be presented for the number of patients in each interval.

Cumulative dose and average daily dose

Cumulative dose for any component of study treatment is defined as the total dose of the medication given during the study treatment exposure.

Average daily dose is defined as [Cumulative dose (mg) / Number of dosing days]; drug free day(s) are not counted as dosing days.

Cumulative dose and average daily dose will be summarized using descriptive statistics for each component of study treatment. Patients with no exposure to the study treatment component will be excluded from the corresponding summary.

Dose intensity and relative dose intensity

Dose intensity (DI) for alpelisib for patients with non-zero duration of exposure to alpelisib is defined as follows:

DI (mg / day) = Cumulative dose (mg) / duration of exposure to alpelisib (day),

Planned dose intensity (PDI) is defined as the assigned dose by unit of time planned to be given to patients as per protocol. The PDI for alpelisib is displayed in [Table 2-2](#). Note that DI for alpelisib will also be calculated and will be reported in the units displayed in [Table 2-2](#), whereas duration of exposure itself will be summarized in months.

Table 2-2 Planned dose intensity

Medication	PDI (dose unit/unit of time)
alpelisib	300mg/day

Alpelisib relative dose intensity (RDI) is defined as: $RDI = DI \text{ (dosing unit / unit of time)} / PDI \text{ (dosing unit / unit of time)}$.

Fulvestrant RDI is defined as:

RDI = actual cumulative dose / planned cumulative dose, where planned cumulative dose is defined as $500^* \text{ (# completed D1 in a 28-days cycle)}$ and added by 500 mg if patients completed C1D15.

DI for alpelisib and RDI for alpelisib and fulvestrant will be summarized separately for each of the study treatment component.

Dose reductions, interruptions and delays

The number and percentage of patients with dose reductions, interruptions or delays, and the reasons, will be summarized.

Interruption: An interruption is defined as a 0 mg dose given on one or more days during the period where a patient is not on the “off” part of a treatment cycle, after which > 0 mg dose resumes. For patients who had dose interruption checked but never resumed non-zero dose, the dose interruption will not be counted. For example, in the sequence of 300 mg – 0mg (dose break) -0mg (dose interruption) – 0 mg (dose permanently discontinuation) the 0mg (dose interruption) will not be counted as dose interruption. Interruptions will be summarized for each component of the study treatment. **Delay:** A special case of alpelisib interruption occurs at the start of a new cycle, after a planned rest period. It will be determined based on alpelisib dose administration record where a planned dose break is followed by a dose interruption. Such instances will be identified as a subset of the interruptions and will be summarized separately as dose delays.

Reduction: A reduction is defined as a decrease from the previous non-zero dose to another non-zero dose less than protocol planned dose, even if this decrease has been directly preceded by an interruption. For example, in the sequence of alpelisib 300mg – 0mg – 150mg, the 150mg dose will be counted as a reduction.

If due to dosing error, a patient took a dose during the dosing with a dose that is lower than the previous dose, this will not be considered as dose reduction. For example, a patient took 300 mg from day 1-15, and mistakenly took 150 mg per day on day 15-28 which is supposed to be 300 mg per day. The patient resumed 300 mg dosing on day 29. This will not be considered as dosing reduction.

Dose reductions and interruptions will be tabulated separately. No dose escalations or dose modifications are allowed with fulvestrant. No dose escalation will be allowed for alpelisib as alpelisib is to be started at the maximum recommended daily dose according to the SmPC. Thus, Dose escalations are not allowed according to the protocol and will not be counted in these summaries.

Missing data: If dose is recorded but frequency is missing or entered as 'none', it is assumed that the study drug was taken as per-protocol.

Discontinuation of study treatment components

The reasons for discontinuation of alpelisib will be summarized, based on the information on the alpelisib DAR eCRF/eDiary for patients who have the "dose permanently discontinued" box checked.

Partial discontinuation: A partial discontinuation is defined as the event when the last nonzero dose of alpelisib is more than 21 days before the last non-zero dose of fulvestrant when the permanent discontinuation checkbox is checked in the alpelisib DAR page. Partial discontinuation of alpelisib will be summarized.

Prohibited Medication

Refer clinical study protocol Section 16.1.2 for the list of Prohibited Medication.

Treatment with the prohibited substances mentioned clinical study protocol Section 16.1.2 will be identified in the database as protocol deviations.

Some patients may take Prohibited substances during the treatment period so these concomitant medications will be selected via programming and tabulated and listed in the Clinical Study Report.

Number of patients who are receiving prohibited medication with percentage will be summarized. Clinical review of individual study data will be performed in order to identify those anti-neoplastic medications which are considered disallowed.

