4. Imaging assessments at baseline to be performed from -28 days to -1 day before Cycle 1, Day 1. Depending on clinical practice and feasibility, assessments scheduled at Day 1 of Cycle 4, Cycle 7, and Cycle 10 can be either performed on the day of the visit or in the week prior to the visit. Tumor assessment and response will be performed by RECIST v1.1 criteria
5. During treatment period, questionnaires to be performed in the week preceding Day 1 of Cycle 4, Cycle 7, and Cycle 10. The baseline completion, should occur between screening and Cycle 1, Day 1, before trial treatment administration
6. Through dedicated questions in the e-diary
7. Through Novartis standard Trial feedback Questionnaire (TFQ) administration
8. Laboratory assessments at baseline to be performed from -14 days to -1 day before Cycle 1, Day 1. Depending on clinical practice and feasibility, laboratory assessments are scheduled at Day 1 of Cycle 4, Cycle 7, and Cycle 10 can be either performed on the day of the visit or in a 3 day window prior to the visit.
9. During treatment period, the Day 1 of each cycle is considered as the day of fulvestrant injection.

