12.5.3 Compliance with treatment and adherence to procedures

Number of patients with missed doses, adjusted dose, interruptions and discontinuations and reason why will be summarized descriptively.

Overall compliance will be summarized descriptively overall and by categories ($\leq 80\%$, $80 >$ and $< 100\%$, and $\geq 100\%$). Overall compliance will assess the degree of correspondence of the actual dosing history with the prescribed drug regimen. Detail of overall compliance calculation will be provided in the SAP.

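### The fulvestrant relative dose intensity in SAP 2.3.2.5 counts completed rather than scheduled injections, so on the ordinary reading missed visits cancel out; the compliance formula the protocol defers to the SAP is absent

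*SAP*

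**What the plan says.** **Fulvestrant ratio.** SAP 2.3.2.5 gives "RDI = actual cumulative dose / planned cumulative dose, where planned cumulative dose is defined as" 500 mg times the number of completed Day 1s in 28-day cycles, "and added by 500 mg if patients completed C1D15". The SAP does not say what makes a Day 1 or a Cycle 1 Day 15 (C1D15) completed. Protocol Table 8-1, note 9, adds: "During treatment period, the Day 1 of each cycle is considered as the day of fulvestrant injection".

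**Schedule.** Protocol 6.1 plans 500 mg on C1D1 and C1D15, then on Day 1 of each later cycle to Cycle 12. Protocol 6.5 allows no fulvestrant dose modification.

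**Compliance.** Protocol 12.5.3 states: "Overall compliance will assess the degree of correspondence of the actual dosing history with the prescribed drug regimen". It sets three reporting classes, with cut-offs at 80% and 100%, and continues: "Detail of overall compliance calculation will be provided in the SAP". SAP Table 1-1 and SAP 2.5.1 both send this endpoint to 2.3.2.5 and nowhere else. The outputs that section announces are: "Duration of study treatment exposure, cumulative dose, dose intensity (DI) and relative dose intensity (RDI) will be summarized". It goes on to cover interruptions, delays, reductions and discontinuation, but gives no compliance formula or classes.

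**Status.** SAP Section 1 says that the trial stopped early for low enrolment, that study data will only be listed, and that changes to planned analyses are reflected in the document. SAP Section 4, on changes from the protocol-specified analyses, reads Not Applicable.

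**The concern.** A relative dose intensity compares what was given with what was planned. The same SAP section says so for alpelisib: "Planned dose intensity (PDI) is defined as the assigned dose by unit of time planned to be given to patients as per protocol". The fulvestrant denominator instead counts what was completed. Since the dose per injection is fixed, an omitted injection is the main way in which fulvestrant can fall short, and that is the shortfall this denominator can remove.

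This bears on the trial's question. After C1D1, injections depend on district nurses or local oncologists, so a missed injection is one way in which the remote model could fail. Compliance is also a secondary objective, and the SAP contains neither a derivation for it nor a statement that it was dropped.

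**Working it through.** The plan states no RDI or compliance figure to reproduce, so the check evaluates the SAP formula directly.

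**Inputs**
- Dose per injection: 500 mg (Protocol 6.1).
- Scheduled injections over 12 cycles: 12 Day 1s + 1 C1D15 = 13, or 13 × 500 = 6500 mg.
- SAP denominator: 500 × (completed Day 1s) + 500 if C1D15 was completed.

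**Reading A: *completed* means visit held or injection given.** Note 9 supports this for Day 1, because it ties Day 1 to the injection. A visit that does not take place leaves both terms.

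**Reading B: *completed* means that the cycle day was reached, for both terms.** The denominator is then the schedule.

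| Case over 12 cycles | Given (mg) | SAP planned, A (mg) | RDI, A | SAP planned, B (mg) | RDI, B = schedule |
|---|---|---|---|---|---|
| All 13 given | 6500 | 6500 | 100% | 6500 | 100% |
| C1D15 visit missed | 6000 | 6000 | 100% | 6500 | 12/13 = 92% |
| One Day 1 visit missed | 6000 | 6000 | 100% | 6500 | 12/13 = 92% |
| Three Day 1 visits missed | 5000 | 5000 | 100% | 6500 | 10/13 = 77% |

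The C1D15 gap is larger with shorter follow-up. With c cycles started and only C1D15 missed, Reading A gives 500c/500c = 100%, while the schedule gives c/(c + 1): 1/2 = 50% for one cycle and 3/4 = 75% for three.

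Reading A has one exception. If a visit is held without an injection and still counts as completed, the planned dose stays in the denominator and RDI falls, to 12/13 = 92% for one such visit over 12 cycles.

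**Compliance.** Protocol 12.5.3 requires actual dosing to be set against the prescribed regimen and leaves the formula to the SAP. Both SAP cross-references lead to 2.3.2.5, where none is given. This gap does not depend on how *completed* is read.

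**The case against.** **The word may mean something else.** Read as day reached for both terms, the SAP ratio equals the schedule-based value and nothing is wrong. SAP Section 1 places further programming specifications in a separate document, which may define the term. This stands. The error is therefore conditional for C1D15 as well as for Day 1, and a reader should not infer that RDI can never fall for a missed C1D15.

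**Missed injections appear elsewhere.** SAP 2.3.2.5 will summarize interruptions for each treatment component. A fulvestrant dose recorded as 0 mg and later resumed is therefore captured, with its reason. All eCRF data (SAP 2.1) and all visit data (SAP 2.5.1) are listed. This largely stands: individual omissions remain visible whatever the ratio shows. It does not make the ratio correct, and an interruption that is never followed by a resumed dose is not counted.

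**Little will be computed.** With data to be listed only, the sentence that RDI will be summarized may be left over from before termination. This stands as a limit on impact. The rule is still in the SAP, however, and Section 4 records no change.

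**RDI is not compliance.** Because the compliance endpoint points to this section, a reader might infer that RDI is meant to serve as compliance, so that a participant at 77% would be reported in the class for 100% and above. The documents do not say this. Nor do they support calling the alpelisib RDI an error: it is a stated exposure measure, and nothing labels it compliance.

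**Conclusion.** The point holds in limited form, and its severity is minor.

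1. In the ordinary sense of *completed*, the fulvestrant RDI stays at 100% when visits are missed, against 92% for one missed C1D15 and 77% for three missed Day 1 visits over 12 cycles. This assumes that the visit did not take place and that the participant remained on fulvestrant. If *completed* means day reached for both terms, there is no error. The SAP does not settle which is meant, so confidence in the numerical effect is moderate.
2. The overall compliance calculation that the protocol defers to the SAP is absent, and its omission is not recorded. This holds on any reading.

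The consequence is small. The ratio misleads only if RDI is output, and the underlying dosing and visit records are to be listed. A reader might infer that missed injections would go unseen in the report; the listings and the interruption summaries do not support that.

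**What to change.** 1. Define planned cumulative fulvestrant dose as 500 mg × injections scheduled per protocol (C1D1, C1D15, then Day 1 of each later cycle), whether or not given. Count up to the earliest of recorded fulvestrant discontinuation, death, last contact or the end of Cycle 12. This removes the undefined word.

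2. State how late injections that move later cycles are counted. On fixed dates, C12D1 falls on day 1 + 11 × 28 = 309 and Cycle 12 ends on day 12 × 28 = 336. A single 14-day shift puts C12D1 on day 323, still inside. A cumulative 28-day shift puts it on day 337, so a participant eventually given all 13 injections would score below 100% unless the rule allows for the shift.

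3. Either define compliance per drug as dose taken divided by dose prescribed and list it per participant, or state in SAP Section 4 that compliance, and RDI if it is not output, is not derived because of early termination.

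**Cost.** A small change to wording and programming, using dosing and diary data already collected. The second option in step 3 takes one sentence. Reported fulvestrant RDI may fall below 100%.

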2.3.3 Prior, concomitant and post therapies

Prior anti-neoplastic therapy

Any prior anti-neoplastic medications, radiotherapy or surgery (biopsy and non-biopsy separately) will be listed for each patient.

Separate listings will be produced for prior anti-neoplastic medications, radiotherapy, and surgery.

Concomitant therapy

Concomitant therapy is defined as all interventions (therapeutic treatments and procedures) besides the study treatment that were administered to a patient, coinciding with the study assessment period (even if started before the study assessment period).

Concomitant medications will be coded using the World Health Organization (WHO) Drug Reference Listing (DRL) dictionary that employs the WHO Anatomical Therapeutic Chemical (ATC) classification system.

All concomitant therapies will be listed. Any concomitant therapies starting and ending prior to the start of study treatment or starting more than 30 days after the last date of study treatment will be flagged in the listing. The safety set will be used for all concomitant medication tables and listings.

Any anti-neoplastic therapy administered concomitantly with study treatment will be listed. .

2.3.4 Protocol Deviations

The number and percentage of patients in the FAS and safety with any protocol deviation will be tabulated by deviation category (as specified in Data Management Plan of the study).

All protocol deviations as well as protocol deviations leading to exclusion from FAS and SAF will be listed.

2.4 Analysis supporting primary objective(s)

All efficacy analyses will be performed on the set of Full Analysis Set. Primary efficacy and safety analyses will be conducted at the end of study.

2.4.1 Primary endpoint(s)

The primary objective of the trial is the participant satisfaction with the DCT experience.

The Trial Feedback Questionnaire (TFQ) is a brief, validated patient questionnaire designed to capture patient trial experience independent of disease and treatment.

Participants will be asked to complete the TFQ to provide feedback on their clinical trial experience. TFQ is divided in 3 parts: Part A – Participant experience before they started the trial; Part B – Participant experience during the trial; and Part C – Participant experienced at the end of the trial.

Participant satisfaction will be assessed at the start of the trial, every 12 weeks or monthly in between visits when full questionnaire is not dispensed during conduct, and at the end of the trial through the TFQ. All of the questions:

Question with five point Likert scale responses: Strongly disagree to Strongly agree;

Question with three point Likert scale responses: Many difficulties to no difficulties;

Question with three point Likert scale responses: Too little/too much and acceptable;

And question with two point Likert scale responses: Yes and no range in score from 1 to 5.

Question with five point Likert scale responses will be scored as 1(worst response), 2, 3, 4 and 5 (best response). Question with three point Likert scale responses will be scored from as 1(worst response), 3 and 5 (best response). Question with two point Likert scale responses will be scored as 1(worst response) and 5(best response). Question A3a and C4a will not have score as question asked in subjective manner.

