11.2 Database management and quality control

Novartis personnel (or designated contract research organization) will review the data entered by investigational staff for completeness and accuracy. Electronic data queries stating the nature of the problem and requesting clarification will be created for discrepancies and missing values and sent to the investigational site via the EDC system. Designated investigator or site personnel are required to respond promptly to queries and to make any necessary changes to the data.

Concomitant treatments and prior medications entered into the database will be coded using the World Health Organization (WHO) Drug Reference List, which employs the Anatomical Therapeutic Chemical classification system. Medical history/current medical conditions and adverse events will be coded using the MedDRA terminology.

The telemedicine platform will be the source document for the ePROs.

Once all the necessary actions have been completed and the database has been declared to be complete and accurate, it will be locked and made available for data analysis. Any changes to the database after that time can only be made after written agreement by Novartis development management.

Additional information will be included in a separated operation manual.

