RAP	Reporting & Analysis Process
RDI	Relative Dose Intensity
RECIST	Response Evaluation Criteria in Solid Tumors
SAE	Serious Adverse Event
SAP	Statistical Analysis Plan
SAS	Statistical Analysis System
SGLT2	sodium glucose co-transporter 2
SOC	System Organ Class
SMQ	Standardized MedDRA Queries
TBIL	Total bilirubin
TFLs	Tables, Figures, Listings
TFQ	Trial Feedback Questionnaire
ULN	Upper Limits Of Normal
WHO	World Health Organization

1 Introduction

This document describes the detailed statistical methodology to be used for the Clinical Study Report (CSR) for the analysis of study CBYL719A03201, open-label, multicenter, pilot-trial evaluating the safety and utility of a hybrid decentralized clinical trial (DCT) approach using a TELEmedicine platform in patients with HR-positive/HER2-negative advanced breast cancer with a PIK3CA mutation treated with alpelisib – fulvestrant.

The content of this SAP is based on CBYL719A03201 Protocol Amendment version 01, dated 15Jun2021). All decisions regarding final analysis, as defined in the SAP document, have been made prior to database lock of the study data.

CSR deliverables (shells for tables, figures, listings) and further programming specifications are described in Tables Figures and Listings (TFL) shells and Programming Datasets Specifications (PDS) documents, respectively.

This study terminated early due to very low rate of enrollment, which made it no longer feasible to continue with the trial; which meant there was insufficient data to perform the planned statistical analyses so study data will be listed only. This SAP amendment was issued after the decision to terminate the study; therefore, the changes to planned analyses are reflected in this document.

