2.1 Data analysis general information

The data will be analyzed by Novartis according to the data analysis section 12 of the study protocol which is available in Appendix 16.1.1 of the CSR. Important information is given in the following sections and details are provided, as applicable, in Appendix 16.1.9 of the CSR.

Statistical analysis will be performed using Statistical Analysis System (SAS)® (SAS Institute, North Carolina), Version 9.4 or higher.

Summary statistics for continuous variables will generally include the number of patients (n), mean, standard deviation, minimum, lower quartile, median, upper quartile, and maximum. Summary statistics will also be presented graphically wherever applicable. For discrete (categorical or binary) variables, the number and percentage of patients in each category will be presented. 95% CIs presented will be 2-sided unless otherwise specified. No formal statistical testing of hypothesis are planned to be performed.

All statistical analyses will be performed under the direction of Novartis personnel. It is planned that the data from all centers that participate in this study will be used. Trial duration is planned to be 12 cycles of 28 days of treatment each. Cut-off date will be Last Patient Last Visit (LPLV) is scheduled as per trial.

The statistical results will be displayed using tables, figures and listings (TFLs). Listings will include all data collected in the eCRF. When dates are imputed, a flag should be provided to show that this is imputed rather than an actual date. In listings, the imputed dates are reported in their original format before imputation. In general, patient listings will be sorted by patient number and assessment date (and time), if applicable.

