2.4.2 Statistical hypothesis, model, and method of analysis

No formal statistical tests will be performed. No imputation procedures will be applied for missing items or missing assessments.

TFQ scores for each patient for each timepoint will be listed.

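### Does it matter that SAP 2.4.1 does not say which score goes to 'too little' and which to 'too much' on the three-point TFQ items?

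*SAP*

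**What the plan says.** SAP 2.4.1 describes the TFQ answer formats: five-point agreement items, three-point items running from many difficulties to none, a second three-point type given as "Question with three point Likert scale responses: Too little/too much and acceptable", and yes/no items. It then sets one rule for both three-point types: "Question with three point Likert scale responses will be scored from as 1(worst response), 3 and 5 (best response"). The only stated exemptions are two items: "Question A3a and C4a will not have score as question asked in subjective manner".

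SAP 2.4.2 gives the output: "TFQ scores for each patient for each timepoint will be listed". It rules out formal tests and imputation. SAP 2.9.4 only refers back to 2.4.2. The SAP introduction explains that enrolment was too slow to continue, and that "there was insufficient data to perform the planned statistical analyses so study data will be listed only".

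Protocol 8.5.1.4 describes the questionnaire as validated and cites a publication whose title covers its scoring. Protocol 12.4.2 planned item-level descriptive statistics. Neither protocol section gives a score for any answer.

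**The concern.** A 1/3/5 rule needs a worst, a middle and a best answer. The difficulty items have that order. The other three-point type, as the SAP words it, has one good answer and two complaints in opposite directions. If 'acceptable' takes the 5, using all three values gives one complaint a 3 and the other a 1, so one counts as milder than the other. The SAP gives no reason for such a ranking and does not say which complaint is the milder. Two programmers working from 2.4.1 alone could list different scores for the same answer.

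This is the primary endpoint, and scores are the only TFQ output named in 2.4.2. Had item means or a satisfaction total been reported, the choice of key would have moved them.

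**Working it through.** **Inputs.** The answer formats, the rule and the two exemptions come from SAP 2.4.1, and the use of the scores from SAP 1 and 2.4.2. The administration schedule is Protocol Table 8-5. The plan gives no figure to reproduce.

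**Possible keys.** Three answers and three values allow 3 × 2 × 1 = 6 assignments. Setting 'acceptable' = 5 (the natural reading, though not printed) leaves 2. Written as (too little, too much), they are (1, 3) and (3, 1). If the slash joins both complaints into one bad pole, two more keys arise: (1, 1), and (3, 3), which leaves the stated worst score unused. Under any of these, 'acceptable' is 5 and a complaint is 1 or 3. The spread across readings is 3 − 1 = 2 points. It measures ambiguity in the text, not an error in any result.

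**What a summary would have shown.** Assume 20 participants (the planned number), with 14 answering 'acceptable' and 6 'too little':

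- too little = 1: (6 × 1 + 14 × 5)/20 = 76/20 = 3.8
- too little = 3: (6 × 3 + 14 × 5)/20 = 88/20 = 4.4

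With 3 'too little' and 3 'too much':

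- either 1/3/5 key: (3 × 1 + 3 × 3 + 14 × 5)/20 = 82/20 = 4.1
- both complaints = 1: 76/20 = 3.8
- both complaints = 3: 88/20 = 4.4

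The item mean could therefore differ by 4.4 − 3.8 = 0.6 between keys. These answer counts are invented for illustration, and the current SAP reports no such mean.

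**What is actually produced.** Table 8-5 gives Part A once, Part B before Cycles 4, 7 and 10, and Part C once. An affected item thus yields 1 to 3 listed scores per participant. The count is not firm. SAP 2.4.1 describes monthly assessment between the full questionnaires as also made through the TFQ, while the notes to Protocol Table 8-1 assign those months to e-diary questions. The documents do not say how many items are affected or in which part they sit. Each score appears as one entry in a patient listing and feeds no further calculation.

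**Where a key could be.** SAP 1 says that "further programming specifications are described in Tables Figures and Listings (TFL) shells and Programming Datasets Specifications (PDS) documents", and Protocol 8.5.1.4 cites the scoring publication. Neither source can be read here. The absence of a TFQ source from the SAP's four-entry reference list proves little: the scoring and validation sources cited for the EQ-5D-5L and BPI-SF in SAP 2.9.2 and 2.9.3 are missing from it too.

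**The case for a change.** The strongest case for a change is that one sentence would make the primary-endpoint listing reproducible from the SAP alone, with no new data. The scoring paragraph remains in the SAP amendment issued after the decision to stop, so it is live text. SAP 2.9.1 names a scoring manual for the EORTC QLQ-C30, and 2.4.1 names none for the TFQ. Reading the slash as one pooled bad answer sits awkwardly with the three-point label. Raw answers may not be there to resolve a doubtful score: SAP 2.1 says "Listings will include all data collected in the eCRF", but Protocol 11.2 says "The telemedicine platform will be the source document for the ePROs", and 2.4.2 promises only scores.

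Much of this stands. The mapping is not printed or cross-referenced, and the three-point label does strain the pooled reading. The worry about raw answers is weaker, because Protocol 8.6.1 places ePRO capture and electronic data capture on the same telemedicine platform, although the documents do not settle the matter.

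What does not follow is a need to amend. Leaving the items unscored, or setting both complaints to 1, could override a key that already belongs to the questionnaire, and nobody can judge that without seeing the items. Printing an existing key would be tidier but would change no result.

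**Conclusion.** No change to the plan. SAP 2.4.1 leaves out a detail that the analysts can supply from the questionnaire's own key or the dataset specification. The ambiguity is at most 2 points on an individual listed score, and it reaches no mean, total, threshold, test or conclusion.

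This rests on two points in the SAP: the data are listed only, and no TFQ composite is defined. It also assumes that whoever programs the scores has the questionnaire and its scoring source, which is reasonable but cannot be confirmed from the documents. If these scores were ever averaged or summed for a report, the key would matter and would have to be shown beside the result.
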